5.2 Exclusion Criteria

There are no exclusions based on economic status, gender, race, or ethnicity. An individual who meets any of the following criteria will be excluded from participation in this study:

1. Vulnerable populations who in the opinion of the investigator are unable to give Informed Consent for reasons of incapacity, immaturity, adverse personal circumstances or lack of autonomy.
2. History of prior non-compliance to prescribed therapy or presence or history of significant psychiatric condition (e.g., drug or alcohol addiction, psychosis, schizophrenia), or cognitive issue which would in the opinion of the investigator, make it difficult for the patient to comply with the study procedures or follow the investigators instructions.
3. Populations for whom in the opinion of the investigator, incentive spirometry is deemed inappropriate due to medical condition or otherwise.
4. Pregnant individuals due to low likelihood of meeting inclusion criteria 4 in section 5.1.

Licensed medical professionals on the clinical team will follow proper procedures in determining if the individual is consenting. Proper procedures entail doing all of the following: giving a patient adequate information concerning the study, providing adequate opportunity for the patient to consider all options, responding to the patient's questions, ensuring that the patient has comprehended this information, obtaining the patient's voluntary agreement to participate and, continuing to provide information as the patient or situation requires. There will be ample opportunity for the patient to ask questions. In the event that the patient is in a vulnerable population and unable to provide consent, they will not be eligible to participate in the study and thus will not be screened. If the individual is not able to provide informed consent or if consent is not certain due to impairments or other factors, they will not be considered for study participation. In the event that the patient is in a vulnerable population and unable to provide consent, they will not be eligible to participate in the study and thus will not be screened.

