7.2 Participant Discontinuation/Withdrawal from the Study

Participants are free to withdraw from participation in the study at any time upon request.

An investigator may discontinue or withdraw a participant from the study for the following reasons:

- If the participant meets any of the exclusion criteria (either newly developed or not previously recognized) that precludes further study participation.
- If the participant insists on using the standard of care IS device.

The reason for participant discontinuation or withdrawal from the study will be recorded by the study team. Given that none of the aforementioned reasons constitutes an adverse event, it may be the case that no further reporting is necessary. Subjects who sign the informed consent form but do not receive the digital IS may be replaced. Subjects who sign the informed consent form and receive the digital IS, and subsequently withdraw, or are withdrawn or discontinued from the study, will not be replaced.

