8.3 Adverse Events and Serious Adverse Events

8.3.1 *Definition of Adverse Events (AE)*

An adverse event is any undesirable experience associated with the use of a medical product in a subject. No adverse events are expected since the device is of nonsignificant risk. The device does not introduce energy to the patient. In addition, voltages related to the device electronics are regulated via appropriate circuitry on board the device.

8.3.2 *Definition of Serious Adverse Events (SAE)*

Not applicable.

8.3.3 *Unanticipated Adverse Device Effect (UADE)*

A UADE is any serious adverse effect on health or safety, or any life-threatening problem or death caused by, or associated with, a device, if that effect, problem, or death was not previously identified in nature, severity, or degree of incidence in the investigational plan or application, or any other unanticipated serious problem associated with a device that relates to the rights, safety, or welfare of subjects.

8.3.4 *Classification of an Adverse Event*

8.3.4.1 *Severity of Event*

Not applicable, no adverse events are defined given the minimal risk of device intervention.

8.3.4.2 *Relationship to Study Intervention*

Not applicable, no adverse events are defined given the minimal risk of device intervention.

8.3.4.3 *Expectedness*

The principal investigator will be responsible for determining whether an adverse event (AE) is expected or unexpected. An AE will be considered unexpected if the nature, severity, or frequency of the event is not consistent with the risk information previously described for the investigational device. However, once again, no adverse events are expected with the described device intervention.

8.3.5 *Time Period and Frequency for Event Assessment and Follow-Up*

No adverse events are expected related to the device, device intervention procedure, or study as a whole. As such, no follow-ups will take place.

8.3.6 *Adverse Event Reporting*

No such reporting will occur given that no adverse events are expected or reasonably probable. In the highly unlikely case of an AE, it will be reported to the principal investigator. The principal investigator will subsequently submit appropriate documentation to the IRB within a timely fashion, as dictated by Penn IRB policy.

8.3.7 *Serious Adverse Event Reporting*

See previous section.

8.3.8 *Reporting Events to Participants*

Not applicable.

8.3.9 *Events of Special Interest*

Not applicable.

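### Section 7.2 rules out adverse-event status for every listed withdrawal reason, but a newly developed condition associated with device use would be an adverse event under 8.3.1

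*Combined protocol and SAP*

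**What the plan says.** Section 7.2 of the combined protocol and SAP opens with the participant's right to leave: "Participants are free to withdraw from participation in the study at any time upon request". It then gives two reasons for which an investigator may withdraw a participant. The first is "If the participant meets any of the exclusion criteria (either newly developed or not previously recognized) that precludes further study participation". The second is that the participant insists on the standard-of-care spirometer. Two sentences on handling follow: "The reason for participant discontinuation or withdrawal from the study will be recorded by the study team", and then "Given that none of the aforementioned reasons constitutes an adverse event, it may be the case that no further reporting is necessary".

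Section 5.2, exclusion 3, reads "Populations for whom in the opinion of the investigator, incentive spirometry is deemed inappropriate due to medical condition or otherwise".

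Section 8.3.1 gives the protocol's definition: "An adverse event is any undesirable experience associated with the use of a medical product in a subject". It sets no severity threshold.

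**The concern.** The last of these sentences in 7.2 settles by declaration something that depends on the individual case. It takes as given that no listed reason is an adverse event and concludes that further reporting may be unnecessary. A study team member who follows it has no prompt to ask whether the condition behind a withdrawal was associated with the device.

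What is at stake is recognition of events. Section 10.1.2 allows the principal investigator to suspend or stop the study if participants are found to be at unexpected or unacceptable risk. That judgement is weaker if a device-associated condition is filed only as a withdrawal reason. There is also an asymmetry. Section 5.4 asks for any serious adverse event to be recorded for screen failures, who are never evaluated with the device. Section 7.2 makes no matching request for patients who used the device and were then withdrawn.

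**Working it through.** The plan gives no figure on this point and none is needed. The check sets the sections side by side.

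**Step 1: does a listed reason include a medical condition arising on study?** The first reason in 7.2 reaches all the exclusion criteria and expressly includes newly developed ones. Exclusion 3 covers patients for whom "incentive spirometry is deemed inappropriate due to medical condition or otherwise". So a condition that arises after surgery, while the patient is using the device, can be a listed reason. Section 7.2 gets there only by reference to 5.2, so the two must be read together.

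**Step 2: can that condition be an adverse event under 8.3.1?** The definition asks for an undesirable experience and an association with use of the product. There are two cases:

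- The condition comes from surgery or underlying disease and is not associated with device use. It falls outside 8.3.1, and 7.2 is consistent with the definition.
- The condition is associated with device use. It meets 8.3.1, and 7.2 contradicts the definition.

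The statement in 7.2 makes no exception for the second case, so it is wrong there and only there.

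**Step 3: does another section tell the two cases apart?**

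- 7.2 has the reason recorded, but assigns nobody to judge whether it was an adverse event.
- 8.3.4.1 and 8.3.4.2 mark severity and relationship assessment not applicable. Relationship is exactly what separates the two cases.
- 8.3.4.3 has the principal investigator judge whether an adverse event is expected. That presupposes the event has already been identified as one.
- 8.3.6 begins "No such reporting will occur given that no adverse events are expected or reasonably probable". It then provides that an adverse event, should one occur, goes to the principal investigator and on to the IRB.
- 8.4.2 sends unanticipated problems to the principal investigator within 48 hours, and 8.5 applies 21 CFR 812.150 to device safety reporting. Both start from an event that someone has recognised.
- 8.3.5 provides no follow-up and 9.4.4 plans no safety analysis.

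No section requires a withdrawal to be checked against 8.3.1.

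**The case against.** The strongest reply is that 7.2 is hedged and does not stand alone. It says only that reporting may be unnecessary, it keeps the reason on record, and 8.3.6, 8.4.2 and 8.5 all remain in force. Patients are inpatients with routine oxygen saturation and pain scoring (8.1). The principal investigator monitors patient safety and device usage on site at least once (10.1.6). A complaint indicating unexpected risk is reportable under 8.4.2. Meeting an exclusion criterion can also be seen as an administrative reason, with any adverse event being the separate occurrence behind it. In addition, the device is described as minimal risk.

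Much of this stands, and it rules out several stronger readings that a reader might infer:

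- *That the statement is wrong for every newly developed condition.* It is not. Exclusion 3 concerns incentive spirometry in general, and a new contraindication after lung resection may have nothing to do with the device.
- *That such an event will go unreported, or could never be recovered.* The documents support only that it can be missed. The reason is on file, recognised events have a route, and patients complete a survey on their experience at discharge.
- *That withdrawal is the main way a device problem would surface.* The documents do not say so, and complaints, routine observation and the survey are alternatives.
- *That withdrawal on request is also declared not to be an adverse event.* The sentence most naturally refers to the two listed investigator reasons. The right to withdraw is stated before that list.
- *That a reported event rate among the 30 patients would be biased.* Section 9.4.4 plans no safety analysis, so there is no planned rate to bias.

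What the reply does not answer is step 3. Every route it relies on begins after recognition, while 7.2 discourages recognition and 8.3.4.2 removes the assessment that would supply it. A low expected frequency makes the problem rarer but does not make the sentence correct.

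**Conclusion.** The point holds in a limited form. The blanket statement in 7.2 conflicts with 8.3.1 for one subset: newly developed exclusion-3 conditions that are associated with device use. For that subset, an event can be recorded only as a withdrawal reason without being recognised as an adverse event. The conclusion rests on the text alone and assumes no event frequency. Its size cannot be quantified, because the documents give neither an expected number of withdrawals nor an expected event rate. This is a rule as written that can misclassify an event, and it should be corrected. It does not show that harm is being concealed or is likely. No position is taken on which conditions should end device use.

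**What to change.** Make these changes in one edit:

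1. Delete the sentence in 7.2 that denies adverse-event status to the listed reasons.
2. Replace it with a rule for every withdrawal after device receipt, including withdrawal on request. The principal investigator records whether the reason is, or results from, an adverse event (8.3.1) or an unanticipated adverse device effect (8.3.3), and its relationship to the device. Any such event is reported under 8.3.6, 8.4 or 8.5 as applicable.
3. List withdrawals by reason and by adverse event yes/no in the study report.
4. Reconcile 8.3.4.2, which marks relationship assessment not applicable, and the opening of 8.3.6, which says no reporting will occur, with the new rule. Without this step, 7.2 would send events to a section that begins by disclaiming reporting.

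Withdrawal on request is included because a patient may ask to leave after an undesirable experience with the device. The present sentence need not cover that case for the check to be useful.

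The cost is a short adverse-event and relationship entry on the withdrawal record, a simple listing, and matching wording in two other sections. The event count may then be above zero. The criteria for withdrawing a patient, and when that happens, are unchanged.

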7.3 Lost To Follow-Up

Not applicable, no follow-up for study participants.

8 STUDY ASSESSMENT AND PROCEDURES

8.1 Efficacy Assessments

Study Procedures and Evaluations:

- 1) Patient identification and eligibility screening:
 - a. Once a potential participant is identified as already scheduled for a lung resection surgery, the clinical team will determine whether the patient satisfies the eligibility criteria.
 - b. Any additional eligibility criteria that cannot be identified or evaluated via Penn Charts will be reviewed and confirmed by the clinical team following receipt of signed ICF forms.
- 2) Patient visit and informed consent:
 - a. If any additional eligibility criteria need to be screened due to a lack of information in Penn Charts, the patient will be asked relevant questions after providing necessary informed consent to the clinical team.
 - i. This will take place in the doctor's office that is private. Note that in-patient hospital stay will not be billed to the study as the hospital stay is unrelated to participation in the study.
- 3) Patient spirometry testing at the pulmonary function laboratory
 - a. This is already done as part of routine care. This is not a study intervention. Lab results from spirometry testing will be a secondary endpoint.
- 4) Device intervention during patient visit
 - a. After receiving informed consent, during preoperative holding, the clinical team will give the patient one digital IS, facilitate the download of the companion app onto the patient's personal mobile device if applicable, and obtain a baseline inspiratory volume measurement.
 - b. Post-surgery, the clinical team will teach patients how to perform breathing exercises with the digital IS and instruct them regarding the quantity, frequency, and volume of inspiratory breaths to perform throughout their hospital stay.
 - i. While the digital IS is powered on, an auditory and haptic reminder will occur every 15 minutes to remind the patient to perform their breathing exercises. The patient has full autonomy as to when and how often to use the digital IS. Digital IS usage and inspiratory volume data will be collected by the device whenever it is used by the patient.
 - ii. At minimum twice per day, the clinical team will collect pain scores. This is already done as part of routine care. This is not a study intervention.

- iii. Every 4 hours, the clinical team will record a patient's SpO2. This is already done as part of routine care. This is not a study intervention.
- c. At discharge, patients will complete a short survey on their experience with the device and IS performance.
- d. Use of the digital IS, and the resulting analysis on adherence, are the primary outcome of this clinical study. Metrics relating to lung function, including inspiratory volume measures, SpO2, pulmonary function lab testing, and pain scores, are the secondary outcomes of this clinical study.
- e. No other vital sign data will be obtained for the study. No follow-up visits will occur. Any withdrawal from the study will occur during this visit as it is the only visit.

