3 STUDY OBJECTIVES AND ENDPOINTS

OBJECTIVES	ENDPOINTS	JUSTIFICATION FOR ENDPOINTS
Primary		
The primary objective is to evaluate the effect of a multifeatured digital IS and integrated phone app on patient adherence to incentive spirometry. Together the device and app will include the following functions: an auditory and haptic reminder cue, visual and auditory cues to guide exercise completion, exercise gamification, and data tracking and visualization features.	The primary endpoints are totality and consistency of incentive spirometry adherence. Specifically, total adherence is a measure of the number of inspiratory breath attempts performed with the digital IS per day, and the consistency of adherence is a measure of the percent of hours in which at least one inspiratory breath was attempted using the digital IS.	The number and frequency of inspiratory breath attempts with the digital IS will be evaluated to assess patient adherence to incentive spirometry.
Secondary		
The secondary objective is to evaluate metrics relating to lung function to assess post-surgery lung recovery in patients using the digital IS.	The secondary endpoints are postoperative blood oxygen saturation (SpO ₂), postoperative pain scores, preoperative pulmonary function spirometry results, and postoperative inspiratory breath quality. Pain scores will be on a scale from 0 (no pain) to 10 (unbearable pain). Specifically, quality refers to inspiratory volumes achieved over time and the flow rate at which inspiratory breaths were taken.	Blood oxygen saturation, pain scores, preoperative spirometry results, and inspiratory breath quality will be evaluated to assess post-surgery lung recovery in patients using the digital IS.
Tertiary		
The tertiary object is to evaluate patient user experience of the digital IS device.	A tertiary endpoint will be survey responses collected from patients at discharge. Please see attached survey for survey questions.	These will be used to assess user experience of the device and companion app if applicable.

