9.4.2 Analysis of the Primary Efficacy Endpoint(s)

As this is a one-arm study and there are no comparative analyses to be made, all of the primary endpoints will be analyzed to determine the average and standard deviation within the total

patient population. In the event that inspiratory breath data could not be collected or were unreliable because of digital IS power interruptions, mouth obstructions that preclude IS use, or other events that may influence digital IS use or inspiratory breath data collection, data from that day will be excluded for the patient.

9.4.3 *Analysis of the Secondary Endpoint(s)*

No secondary endpoints are dependent on findings of primary endpoints. Average change in blood oxygen saturation and pain scores over time will be calculated across the course of each patient's postoperative stay. The change in volume of inspiratory breaths will also be calculated across the course of each patient's postoperative stay. This will also be evaluated against both the baseline IS measurement taken preoperatively as well as pulmonary function lab results. The average and standard deviation of flow rates and time spent at different flow rates will also be calculated. The time spent below or above the target 200ml/s-800ml/s range will be calculated for each inspiratory breath, and used to measure the percentage of attempted inspiratory breaths that fell within this range. As this is a one-arm study and there are no comparative analyses to be made, all of the secondary endpoints will be analyzed to determine the average and standard deviation within the total patient population.

9.4.4 *Safety Analyses*

Not applicable.

9.4.5 *Baseline Descriptive Statistics*

Not applicable.

9.4.6 *Planned Interim Analyses*

Not applicable.

9.4.7 *Sub-Group Analyses*

Not applicable

9.4.8 *Tabulation of Individual Participant Data*

Individual patient data will be stored with a randomized patient number instead of their name (e.g., 001, 002, etc).

9.4.9 *Exploratory Analyses*

Not applicable.

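### SpO2 change is meant to describe lung recovery, but no oxygen-support status is collected, so recovery and oxygen withdrawal cannot be separated

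*Combined protocol and SAP*

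**What the plan says.** The protocol gives SpO2 a purpose. In the Section 3 table the justification for the secondary endpoints reads "Blood oxygen saturation, pain scores, preoperative spirometry results, and inspiratory breath quality will be evaluated to assess post-surgery lung recovery". Section 8.1 repeats the classification: "Metrics relating to lung function, including inspiratory volume measures, SpO2, pulmonary function lab testing, and pain scores, are the secondary outcomes".

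The readings come from routine care every 4 hours (1.3, 8.1). Section 9.4.3 describes the analysis: "Average change in blood oxygen saturation and pain scores over time will be calculated across the course of each patient's postoperative stay". Across patients, "all of the secondary endpoints will be analyzed to determine the average and standard deviation within the total patient population". Nothing in 9.4.3 restricts, stratifies or adjusts SpO2 by oxygen status.

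On data collection, 8.1 states "No other vital sign data will be obtained for the study". The recorded-data list in 10.1.3 names SpO2, lung-function laboratory results, pain scores, survey responses, age, weight, height and sex, together with the device data and identifiers. The final data set in the same section has blood oxygen saturation as a single item. Section 10.1.8.1 lists what is taken from EPIC. None of these mentions supplemental oxygen, flow, FiO2 or room-air status. Section 6.5 (Concomitant Therapy) is marked not applicable.

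**The concern.** A saturation reading reflects the oxygen being given as well as the lung. If a patient improves and oxygen is withdrawn, its contribution to the reading disappears just as the lung gets better, so the two effects pull in opposite directions. A patient who goes from 97% on oxygen to 95% on room air may have improved, yet enters the summary as -2 points. If oxygen is adjusted to hold saturation steady, the change is near zero whatever the lung has done.

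The plan has no other handle on this. SpO2 is defined as a postoperative endpoint, so change runs within the stay and not from a preoperative saturation. There is also no comparison arm (6.3) in which oxygen practice could be seen. What is at stake is whether the SpO2 summary can carry the lung-recovery meaning that Section 3 assigns to it.

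**Working it through.** The plan gives no figure for SpO2 to reproduce. The 30 patients are a caseload estimate (9.2), hypotheses are marked not applicable (9.1), and no SD or expected change is stated. The check is therefore a reading of the data lists followed by an illustration.

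**1. Is oxygen support collected anywhere?**

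| Place | What it covers | Oxygen support? |
|---|---|---|
| 1.3, 8.1 | SpO2 every 4 hours; oxygen condition of the reading not specified | No |
| 6.5 | Concomitant therapy, not applicable | No |
| 9.4.3 | Average change, then mean and SD | No |
| 10.1.3, recorded data | SpO2 among the named items | No |
| 10.1.3, final data set | Blood oxygen saturation alone | No |
| 10.1.8.1 | Items obtained from EPIC | No |

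**2. How many readings are affected?** One every 4 hours is 24/4 = 6 a day. Over the average stay of 2-3 days (1.1) that is 12 to 18 readings per patient, and at most 7 × 6 = 42 over a week. None has a linked oxygen value.

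**3. What does the planned summary estimate?** For one patient:

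observed change = change at constant oxygen support + (oxygen effect at end − oxygen effect at start).

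If a share p of patients come off oxygen and each loses d points by doing so, the cohort mean is shifted by −p × d.

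**4. Illustration.** Both p and d are assumptions; the documents give neither.

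- p = 0.30, d = 1: shift = −0.30 × 1 = −0.3 points
- p = 0.30, d = 2: shift = −0.30 × 2 = −0.6 points
- p = 0.60, d = 1: shift = −0.60 × 1 = −0.6 points
- p = 0.60, d = 2: shift = −0.60 × 2 = −1.2 points

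The mean has the wrong sign when the true mean gain at constant oxygen is smaller than p × d. On this grid, that means a true gain below 0.3 points at one end and below 1.2 points at the other.

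**5. A wider grid**, again assumed, with a true gain of +2 points, so that observed mean = 2 − p × d:

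| p | d = 1 | d = 2 | d = 3 | d = 4 |
|---|---|---|---|---|
| 0.50 | +1.5 | +1.0 | +0.5 | 0.0 |
| 0.75 | +1.25 | +0.5 | −0.25 | −1.0 |

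The same true recovery can appear as a gain, as no change or as a loss. Without oxygen status a reader cannot tell which case applies. If no patient receives oxygen, p = 0 and there is no shift.

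**The case against.** The strongest reply is that little hangs on this endpoint. SpO2 is one of several descriptive secondary endpoints in an exploratory single-arm study of 30. No decision rule or sample size depends on it. Inspiratory volume is separately compared with the preoperative baseline and the lung-function results (9.4.3), so SpO2 is not the only measure of recovery. Without a control arm, SpO2 change could not be attributed to the device even if oxygen were recorded. All of this stands and limits the weight of the point. It does not remove it, because a descriptive summary should still describe what Section 3 says it describes.

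Three stronger readings are tempting, and the documents do not support them.

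- A reader might infer that the sentence in 8.1 forbids collecting oxygen data. It restricts vital signs, and oxygen delivery is a treatment setting. The evidence for the gap is the lists in 10.1.3 and 10.1.8.1.
- A reader might infer that the bias exceeds the precision of the estimate. The plan computes no confidence interval for SpO2 and gives no SD. With n = 30 the 95% half-width would be t(0.975, 29)/√30 = 0.373 SD. A 1.2-point shift is then 3.2, 1.6 or 1.1 half-widths at an assumed SD of 1, 2 or 3 points, and a 0.3-point shift is only 0.8, 0.4 or 0.3. The comparison depends on the assumptions chosen.
- A reader might infer that restricting the analysis to room-air readings solves the problem. That conditions on recovery: patients still on oxygen contribute few or no readings, and the first room-air value falls at a different time in each patient. With 12 to 18 readings in an average stay, some patients may have no usable change.

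**Conclusion.** The point holds as a limit on interpretation. As written, the plan produces an SpO2 change whose sign and size cannot be read as lung recovery, because the oxygen support at each reading is not in the data to be collected. This rests on one assumption from outside the documents: that some patients receive supplemental oxygen that is reduced during the stay.

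The size is unknown. The −0.3 to −1.2 point range is an illustration from assumed inputs, not an estimate for this study. The documents do not show that the SpO2 result will be wrong, only that it could be near zero or reversed without anyone being able to tell. A reader might also infer that the adherence findings are compromised. They are not: both primary endpoints come from device timestamps and do not use SpO2.

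**What to change.** 1. Add to the data lists in 10.1.3 and to the EPIC extraction in 10.1.8.1 the oxygen support charted at or nearest each SpO2 reading: room air yes or no, and flow or FiO2 where charted.
2. Amend 9.4.3 to report SpO2 by oxygen status, together with the percent of readings on room air by postoperative day. The second summary shows oxygen withdrawal directly.
3. If a room-air-only change is reported, label it as a selected subset and give the number of patients and readings that contribute.
4. If oxygen status cannot be extracted, state in Sections 3 and 9.4.3 that SpO2 change will not be interpreted as lung recovery.

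The cost is one extra item in an extraction already planned, an IRB edit to the data list, and smaller numbers in each oxygen stratum. The documents do not say whether oxygen support is charted with a usable timestamp, so this should be checked before the extraction is specified. No study procedure is added, and no change to clinical oxygen management is implied.
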